## General recommendations to avoid skin toxicities:

	Avoid unnecessary exposure to sunlight and excessive use of soap.
	Avoid bathing in excess; use tepid rather than hot water.
	Use moisturizers regularly; apply thick, alcohol-free and oil-in-water based emollient cream on exposed and dry areas of the body.
	Avoid perfumed products, bubble bath, perfumed soaps, and take breaks from shaving.
•	Use broad-spectrum sunscreen with a skin protection factor (SPF)≥15.
	Wear cotton clothes next to skin rather than wool, synthetic fibers, or rough clothing.
	Use occlusive alcohol-free emollient creams (jar or tub) for treatment of mild/moderate xerosis.
	For scaly areas, use exfoliants (ammonium lactate 12% or lactic acid cream 12%).

#### 8.2.1.2. Diarrhea

Diarrhea has been reported in all Cobimetinib clinical studies in cancer patients. In the Phase I single-agent study (MEK4592g), diarrhea of any grade was reported in 67.0% of patients, 6.1% of patients experienced Grade 3 diarrhea, and no Grade 4 or 5 events were reported as of the data cutoff date. Serious events of diarrhea were reported in 1.7% of patients. In the Phase III study (GO28141), diarrhea was the most common adverse event reported. Diarrhea events of all grades were reported in 56.7% of patients, and Grade 3 or 4 events were reported in 6.3% of patients treated with vemurafenib + Cobimetinib. No Grade 5 events of diarrhea were reported as of the data cutoff date. Serious events of diarrhea were reported in 1.2% of patients treated with

## vemurafenib + Cobimetinib.

Diarrhea can frequently be managed with anti-diarrheal agents but can also progress to clinically significant dehydration and/or electrolyte imbalances with effects on other organs, possibly resulting in renal, hepatic, and/or cardiac failure. Patients should be instructed to promptly contact the investigators if they develop diarrhea. Investigators should treat diarrhea and intervene promptly for patients who appear to be at increased risk of developing significant dehydration, electrolyte imbalances, and/or multi-organ failure. Patients should receive maximum supportive care per institutional guidelines.

Patients should be instructed to promptly report and seek medical evaluation for severe GI signs and symptoms (e.g., sudden onset of severe abdominal pain and fever, hematemesis, hematochezia, melena), and investigators will monitor patients closely for severe GI toxicity, perform appropriate medical evaluation and treatment, and promptly refer to a specialist, if applicable. Patients with known severe ulcer disease should not be administered Cobimetinib.

#### 8.2.1.3. Nausea and vomiting

For nausea and/or vomiting, maximum supportive care, including ondansetron and aprepitant, should be administered at the discretion of the investigator or per institutional guidelines.

#### 8.2.1.4. Alteration in Liver Functions

Liver laboratory test abnormalities, including elevations in AST and/or ALT, have been reported as adverse events and serious adverse events in patients treated with vemurafenib+Cobimetinib. In the Phase III study (G0 28141), liver laboratory test abnormalities reported as Grade 3 adverse events occurred more frequently in patients treated with vemurafenib+Cobimetinib than vemurafenib+placebo (20.5% vs. 15.1%). Liver laboratorytest abnormalities reported as Grade 3 adverse eventsat frequencies 2% higher in patients treated with vemurafenib+Cobimetinib than vemurafenib+placebo included increased ALT (11.4% vs. 6.3%), increased AST (8.3% vs. 2.1%), and increasedalkaline phosphatase (4.3% vs. 1.7%).

In Study MEK4592g, there were no reported adverse events or serious adverse events for clinically significant Grade 4 elevations in liver laboratory tests, and no patient experienced findings suggestive of drug-induced liver injury or liver failure. Generally, elevations in liver laboratory tests were managed effectively with dose modification guidelines. In both study arms of G028141, the majority of Grade 3 liver laboratory test abnormalities resolved.

#### 8.2.1.5. Visual Disturbances

Serous retinopathy (fluid accumulation within the layers of the retina) has been observed with MEKi, including Cobimetinib. The majority of events in Cobimetinib-treated patients were reported as chorioretinopathy or retinal detachment. In the Phase I single-agent study (MEK4592q), also with ocular examinations prescribed for patients reporting visual disturbance, 2.6% of patients (inc luding 1 patient with a Grade 2 event that was not coded at the time of the data cutoff date) experienced serous retinopathy events, all of which were Grade 1 or 2.

In the Phase III study (G028141), with prospective serial ocular examinations, serous retinopathy events were reported more frequently in patients treated with vemurafenib+Cobimetinib than vemurafenibDplacebo (24% vs. 2.1%), and approximately 50% were asymptomatic Grade 1 events. Few patients treated with vemurafenibOCobimeti nib experienced Gra de 3 ocular events (2.8%); the majority of these were managed with dose modification of both Cobimetinib and vemurafenib, and all were resolved or resolving as of the data cutoff date.

Patients with neurosensory detachment of the retina typically present with visual disturbances

such as blurred vision, seeing spots, and photophobia; however, some patients have been asymptomatic. These cases have been reversible and most patients are able to continue treatment at the same or reduced dose, but some have experienced recurrence upon re-challenge and have discontinued study drug. It should be noted that these events of neurosensory detachment have occurred only with doses at or above the MTD.

To address the potential ocular toxicity, patients with a history of RVO or glaucoma, visible retinal pathology, intraocular pressure > 21 mmHg, and predisposing factors to RVO (e.g., uncontrolled hypertension, diabetes, or hyperlipidemia, coagulopathy) within 6 months of protocol enrollment will be excluded. Patients will be asked about any vision changes at each symptom-directed physical examination. All new patients will have complete ophthalmologic examinations performed and interpreted by a qualified ophthalmologist, including visual acuity testing, intraocular pressure measurements by tonometry, slit lamp ophthalmoscopy, indirect ophthalmoscopy, and spectral domain optical coherence tomography. These complete ophthalmologic examinations will be performed at baseline.

For any treatment emergent onset of Grade ≥ 2 visual symptoms or ocular toxicity, Cobimetinib must be interrupted pending diagnostic evaluation, which will include a complete ophthalmologic examination. If RVO is diagnosed, Cobimetinib dosing should be permanently discontinued and the RVO treated per institutional guidelines.

General considerations: Avoid unnecessary	exposure to sunlight,	use sunglasses	in bright
light.		_	

□ Prophylactic management: Frequent use of artificial tear substitutes is strongly recommended.

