- 12. Concurrent treatment with a non-permitted drug as well as foods or supplements that are strong or moderate CYP3A4 enzyme inducers or inhibitors. Any of the above has to be discontinued at least 7 days prior to Cycle 1/ Day 1 of study treatment. See supplemental packet for quidance.
- 13. Requirement of anticoagulant therapy with oral vitamin K antagonists such as Coumadin (warfarin). Low-dose anticoagulants for the maintenance of patency in a central venous access device or the prevention of deep vein thrombosis or pulmonary embolism is allowed. Therapeutic use of low molecular weight heparin is allowed provided patients are safely able to interrupt it prior to biopsy procedures.
- 14. Persisting non-hematological toxicity related to prior therapy that has not reduced to Grade 1 [National Cancer Institute Common Toxicity Criteria for Adverse Events (NCI CTCAE) version 5.0]; however, alopecia and sensory neuropathy Grade ≤ 2 are acceptable and Grade ≤ 2 nonhematological toxicities well controlled with medical management are allowed (for example: hypomagnesemia well controlled on magnesium replacement).
- 15. Known severe (Grade ≥ 3 NCI-CTCAE) hypersensitivity reactions to monoclonal antibodies, or history of anaphylaxis.
- 16. Vaccination within 28 days of the first dose of study drugs and while on trial is prohibited, except for administration of inactivated vaccines (for example, inactivated influenza vaccine).
- 17. Pregnant or breastfeeding females.
- 18. Known current alcohol or drug abuse
- 19. Prisoners or subjects who are involuntarily incarcerated.
- 20. Known psychiatric condition, social circumstance, or other medical condition reasonably judged by the patient's study physician to unacceptably increase the risk of study participation; or to prohibit the understanding or rendering of informed consent or anticipated compliance with scheduled visits, treatment schedule, laboratory tests and other study requirements.
- 21. Known risk factors for ocular toxicity (cobi arm only), consisting of any of the following:
  - presence of serous retinopathy within 6 months of protocol enrollment
  - presence of retinal vein occlusion (RVO) within 6 months of protocol enrollment

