- 7. Significant acute or chronic infections including, among others:
  - Known history of testing positive for human immunodeficiency virus (HIV), or acquired immunodeficiency syndrome (AIDS).
  - Active tuberculosis
  - Positive test for hepatitis B virus (HBV) surface antigen (and/or core antibody) and/or confirmatory hepatitis C virus (HCV) RNA (if anti-HCV antibody tested positive).
- 8. Active autoimmune disease with reasonable possibility of clinically significant deterioration when receiving an immunostimulatory agent:
  - Subjects with Type 1 diabetes mellitus, vitiligo, psoriasis, hypo- or hyperthyroid disease not requiring immunosuppressive treatment are eligible.
  - Subjects requiring hormone replacement with corticosteroids are eligible if the steroids are administered only for the purpose of hormonal replacement and at doses ≤ 10 mg or 10 mg equivalent prednisone per day.
  - Administration of steroids through a route known to result in a minimal systemic exposure (topical, intranasal, intro-ocular, or inhalation) are acceptable.
- 9. Interstitial lung disease that is symptomatic or which may interfere with the detection or management of suspected drug-related pulmonary toxicity.
- 10. Uncontrolled asthma [defined as having 3 or more of the following features of partially controlled asthma within 28 days prior to starting study treatment: Daytime symptoms more than twice per week, any limitation of activities, any nocturnal symptoms/awaking, need for reliever/rescue inhaler more than twice per week, or known lung function (PEF or FEV1) without administration of a bronchodilator that is < 80% predicted or personal best (if known)].
- 11. Current symptomatic congestive heart failure (New York Heart Association > class II), unstable cardiac arrhythmia requiring therapy (e.g. medication or pacemaker), unstable angina (e.g. new, worsening or persistent chest discomfort), or uncontrolled hypertension (systolic > 160 mmHg or diastolic > 100mmHg). Or any of the following occurring within 6 months (180 days) prior to first dose of study drugs: Myocardial infarction, coronary/peripheral artery bypass graft, cerebrovascular accident or transient ischemic attack. (Use of antihypertensive medication to control blood pressure is allowed.)

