- 12. Concurrent treatment with a non-permitted drug (refer to prohibited medication list) as well as foods or supplements that are strong or moderate CYP3A4 enzyme inducers or inhibitors. Any of the above has to be discontinued at least 7 days prior to Cycle 1/ Day 1 of study treatment.
- 13. Requirement of anticoagulant therapy with oral vitamin K antagonists such as Coumadin (warfarin). Low-dose anticoagulants for the maintenance of patency in a central venous access device or the prevention of deep vein thrombosis or pulmonary embolism is

allowed. Therapeutic use of low molecular weight heparin is allowed provided patients are safely able to interrupt it prior to biopsy procedures.

- 14. Persisting toxicity related to prior therapy that has not reduced to Grade 1 [National Cancer Institute Common Toxicity Criteria for Adverse Events (NCI CTCAE) version 5.0]; however, alopecia and sensory neuropathy Grade ≤ 2 are acceptable and Grade ≤ 2 nonhematological toxicities well controlled with medical management are allowed (for example: hypomagnesemia well controlled on magnesium replacement).
- 15. Known severe (Grade ≥ 3 NCI-CTCAE) hypersensitivity reactions to monoclonal antibodies, or history of anaphylaxis.
- 16. Vaccination within 28 days of the first dose of study drugs and while on trial is prohibited, except for administration of inactivated vaccines (for example, inactivated influenza vaccine).
- 17. Pregnant or breastfeeding females.
- 18. Known current alcohol or drug abuse
- 19. Prisoners or subjects who are involuntarily incarcerated.
- 20. Known psychiatric condition, social circumstance, or other medical condition reasonably judged by the patient's study physician to unacceptably increase the risk of study participation; or to prohibit the understanding or rendering of informed consent or anticipated compliance with scheduled visits, treatment schedule, laboratory tests and other study requirements.
- 21. Known risk factors for ocular toxicity, consisting of any of the following (Cobi arm only):
  - presence of serous retinopathy within 6 months of protocol enrollment
  - presence of retinal vein occlusion (RVO) within 6 months of protocol enrollment

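### Section 8.2.1.5 claims ocular exclusions for cobimetinib that exclusion criterion 21 does not contain, so the protocol gives two different eligibility rules for one arm

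*Combined protocol and SAP*

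**What the plan says.** Section 8.2.1.5 (Visual Disturbances) sits in the cobimetinib part of the toxicity chapter. As a measure against ocular toxicity it names "patients with a history of RVO or glaucoma, visible retinal pathology, intraocular pressure > 21 mmHg, and predisposing factors to RVO". It then gives examples of predisposing factors and the consequence: "uncontrolled hypertension, diabetes, or hyperlipidemia, coagulopathy) within 6 months of protocol enrollment will be excluded".

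Exclusion criterion 21 in Section 4.2 opens with "Known risk factors for ocular toxicity, consisting of any of the following (Cobi arm only" and has two items: "presence of serous retinopathy within 6 months of protocol enrollment" and "presence of retinal vein occlusion (RVO) within 6 months of protocol enrollment". The synopsis carries the same criterion ("Known risk factors for ocular toxicity (cobi arm only), consisting of any of the following") with the same two items.

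Three other criteria in Section 4.2 bear on the comparison:

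- Criterion 11 excludes, among current cardiovascular conditions, "uncontrolled hypertension (systolic > 160 mmHg or diastolic > 100mmHg".
- Criterion 8 (criterion 9 in the synopsis), on active autoimmune disease, contains the allowance "Subjects with Type 1 diabetes mellitus, vitiligo, psoriasis, hypo- or hyperthyroid disease not requiring immunosuppressive treatment are eligible".
- Criterion 20 allows exclusion for a medical condition that the study physician reasonably judges to raise the risk of participation unacceptably.

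Note 11 to the study calendar requires a complete eye examination before treatment in the cobimetinib arm, including tonometry and retinal examination. It may be done up to 42 days before treatment starts. Section 5.1 makes registration depend on the criteria in an eligibility checklist, with sponsor review; the checklist is not among the documents.

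**The concern.** The toxicity section states a firm exclusion, and the eligibility section does not carry it out. Sites register patients from the eligibility criteria. If the checklist follows Section 4.2, a patient with glaucoma or a pressure above 21 mmHg meets every named ocular criterion, although 8.2.1.5 says she is excluded. The pre-treatment examination will show the pressure and the state of the retina, but no criterion says what finding disqualifies. Two sites could treat the same result differently.

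Eye toxicity is a recognised risk of this drug. Section 8.2.1.5 reports serous retinopathy in 24% against 2.1% in the Phase III study, where cobimetinib was given with vemurafenib, and in 2.6% in the single-agent Phase I study. It adds that neurosensory detachment was seen only at or above the MTD. This trial gives 60 mg on the 21/7 schedule, which Section 3.7.1.1 reports as the MTD for that schedule. What is at stake is whether a stated protection is actually applied.

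**Working it through.** No arithmetic is involved beyond counting, and the plan gives no figure to reproduce. The check sets the items in 8.2.1.5 against all the criteria in Sections 4.1 and 4.2.

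| Item in 8.2.1.5 | Closest criterion | Covered? |
|---|---|---|
| Past RVO | 21, second item (within 6 months) | Fully, only if the 6-month window in 8.2.1.5 also applies to past RVO; otherwise older RVO is missed |
| Glaucoma | None names it | Only at discretion (20) |
| Visible retinal pathology | 21 (serous retinopathy or RVO within 6 months) | In part |
| Pressure above 21 mmHg | None names it | Only at discretion (20) |
| Predisposing factors to RVO | See below | In part |

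The examples given for the fifth item:

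- Uncontrolled hypertension: criterion 11 covers it when current. The 6-month look-back in that criterion belongs to infarction, bypass graft, stroke and transient ischemic attack, not to blood pressure. If the window in 8.2.1.5 applies to this factor, the match is incomplete.
- Diabetes: no criterion excludes it.
- Hyperlipidemia: no criterion names it.
- Coagulopathy: no criterion names it. Criterion 13 concerns the need for oral vitamin K antagonists, which is a different matter.

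The count: 8.2.1.5 has 5 items, treating the examples as part of the fifth; criterion 21 has 2. Of the 5, 2 (glaucoma and the pressure limit) are named nowhere in the criteria, 2 are covered in part, and 1 (RVO) depends on how the time window is read.

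The 8.2.1.5 sentence also leaves two things open. Its 6-month window may apply to every item or only to the last, and the word 'uncontrolled' may qualify hypertension alone or diabetes and hyperlipidemia as well.

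A line lost when the text was read from PDF is an unlikely explanation, because criterion 21 has the same two items in the synopsis and in Section 4.2. Neither text comes from the amendment record, and no section reconciles them.

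**The case against.** The strongest reply is that Section 4.2 governs and 8.2.1.5 is narrative. The two-item list appears identically in both eligibility sections, and registration turns on the eligibility checklist with sponsor review. The 8.2.1.5 paragraph also looks imperfectly fitted to this trial: it speaks of eye examinations for all new patients, where the calendar limits them to the cobimetinib arm. This makes the narrow list a plausible intention. It does not remove the contradiction. The sentence is worded as a rule, its paragraph also prescribes the baseline eye examination, and no section says which text prevails. If Section 4.2 does govern, the protocol claims a safeguard it does not apply, and the sentence still has to change.

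A second reply is that protection remains. Recent serous retinopathy and recent RVO are excluded. Eye examinations continue on treatment. Section 8.2.1.5 interrupts cobimetinib for Grade 2 or higher ocular toxicity and stops it for RVO. Section 8.5 reports RVO with MEK inhibitors other than cobimetinib. All of this stands and limits the consequence, but on-treatment measures act after exposure and do not settle who may enter.

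Two stronger readings are tempting and are not supported:

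- A reader might infer that nothing in the criteria could keep out a patient with glaucoma or raised pressure. Criterion 20 could, at the physician's discretion. The accurate statement is that no criterion names these conditions or requires exclusion.
- A reader might infer that the type 1 diabetes allowance flatly contradicts 8.2.1.5. It is a carve-out from the autoimmune criterion, not a general grant of eligibility, and it conflicts only if 8.2.1.5 is meant to exclude all diabetes rather than uncontrolled diabetes.

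**Conclusion.** The inconsistency is real in the current text and should be corrected. Section 8.2.1.5 promises exclusions that criterion 21 does not contain, and other criteria fill the gap only in part: current uncontrolled hypertension through criterion 11, anything else through physician judgement under criterion 20.

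Its reach is limited to eligibility and ocular safety in the cobimetinib arm. Sample size and primary analysis do not depend on it. The documents do not give the frequency of the uncovered conditions, so the number of patients affected cannot be calculated. A reader might go further and infer that excluded patients will in fact be registered. The documents do not show that, because the checklist is not available and sponsor review might catch a case.

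The conclusion assumes that the items in the 8.2.1.5 sentence are separate grounds for exclusion, and that the checklist follows Section 4.2. If the checklist already carries the wider list, the practical risk falls but the texts still disagree.

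**What to change.** State one list in the synopsis, Section 4.2 and Section 8.2.1.5. The sponsor has to say which is intended.

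If the wider safeguard is intended:

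- Add glaucoma, pressure above 21 mmHg, visible retinal pathology and the predisposing factors to RVO to exclusion 21, cobimetinib arm only, and keep the two present items.
- State which items the 6-month window applies to, including past RVO.
- State whether 'uncontrolled' qualifies diabetes and hyperlipidemia, and that the type 1 diabetes allowance concerns the autoimmune criterion only.
- Require the result of the baseline eye examination before eligibility is confirmed. Section 5.1 does not name an ophthalmology report among the documents sent for eligibility review, so it should be added there.

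If the narrow list is intended, reword the 8.2.1.5 sentence so that it claims no more than criterion 21.

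Either route costs an amendment; the wider list also needs new checklist wording. It brings the eye examination result forward in the workflow and makes some cobimetinib-arm patients ineligible, in a proportion the documents do not give. It needs no new examination. Criterion 21 concerns known risk factors, so hyperlipidemia and coagulopathy can be taken from the history; the study calendar lists no lipid or coagulation test.

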#### 8.2.1.6. Cardiac Effects

Left ventricular dysfunction may occur with signs and symptoms of cardiac failure, or reduction in left ventricular ejection fraction (LVEF) may be asymptomatic. Without active surveillance for reduction in LVEF, there were no events in this risk category reported in the Phase I single agent study (MEK4592g). In the Phase III study (GO28141), with active surveillance, reductions in LVEF were reported more frequently in patients treated with vemurafenib+Cobimetinib than vemurafenib+placebo (6.7% vs. 2.9%). Of the patients treated with vemurafenib+Cobimetinib, two patients (0.8%) had symptomatic reduction in LVEF and the remaining patients were asymptomatic. One patient in each arm (0.4% each) experienced serious events; these were symptomatic. Most events in patients treated with vemurafenib+Cobimetinib (88%) improved or resolved with management according to the dose modification guidelines. No Grade 4 or 5 events of reduction in LVEF have been reported in Cobimetinib clinical studies as of the data cutoff dates. Reduction in LVEF has also been observed in patients treated with MEKi other than Cobimetinib.

